16.3. Pharmacokinetics

16.3.1. Analysis Population

The analysis population for PK analysis is defined as all subjects who were randomized, were dosed with aducanumab, and had at least 1 measurable aducanumab concentration in serum.

16.3.2. Method of Analysis

The serum concentrations and PK parameters of aducanumab will be summarized descriptively.

16.4. Safety

16.4.1. Analysis Population

The safety population is defined as all subjects who were randomized and received at least 1 dose of aducanumab.

16.4.2. Methods of Analysis

All AEs, laboratory data, ECG, neurological and physical examinations, and vital signs will be evaluated for safety.

16.4.2.1. Adverse Events

Only treatment emergent adverse events (TEAEs) will be presented in the summary tables. Treatment emergent is defined as having an onset date that is on or after the start of study treatment, or as worsening after the start of study treatment.

Incidence of TEAEs will be summarized by treatment group, overall, by severity, and by relationship to study treatment for the randomized treatment period and the LTE period. The summary tables will include incidence estimates for overall system organ class as well as for preferred terms within each system organ class. AEs will be coded using the Medical Dictionary for Regulatory Activities.

16.4.2.2. Clinical Laboratory Results

Clinical laboratory evaluations include hematology, blood chemistry, and urinalysis. Laboratory data will be summarized using shift tables. Shifts from baseline to high/low status for hematology and blood chemistry parameters and shifts from baseline to high/positive status for urinalysis will be presented. In addition, the shift from baseline to the maximum postbaseline value and the shift from baseline to the minimum postbaseline status will be presented for each laboratory test by treatment group. Also, summaries of laboratory values categorized based on common toxicity criteria grade will be created. Summary statistics for actual values and change from baseline will also be presented for quantitative laboratory data.

CONFIDENTIAL

The information contained herein may not be used, disclosed, or published without the written consent of Biogen MA Inc.

16.4.2.3. Vital Signs and ECGs

The analysis of vital signs and ECGs will focus on clinically relevant abnormalities.

16.4.2.4. Columbia Suicide Severity Rating Scale

C-SSRS data will be summarized by treatment group.

16.5. Immunogenicity Data

16.5.1. Analysis Population

The analysis population for immunogenicity is defined as all subjects in the safety population who have at least 1 postdose sample evaluated for immunogenicity.

16.5.2. Methods of Analysis

Antiaducanumab serum antibodies will be summarized will be summarized for each group and overall.

16.6. Interim Analyses

An interim analysis for the primary endpoint may be performed.

16.7. Sample Size Considerations

Based on the data from Study 221AD103, 2 out of 185 subjects (1%) experienced serious ARIA events resulting in hospitalization within the first 12 months of treatment with aducanumab. In addition, there were no deaths or persistent significant disability due to ARIA. Of the 185 subjects, 31 subjects were in the 10 mg/kg titration group, and none of them experienced clinically impactful ARIA. By applying the current definition of clinically impactful events as the primary endpoint to this study, a low incidence of clinically impactful ARIA events is expected to be observed during the study.

This is an estimation study. No formal hypothesis testing is planned. In Study 221AD103, of the 185 subjects, 20 subjects developed asymptomatic moderate ARIA-E and 1 subject developed severe asymptomatic ARIA-E. In order to enroll 25 subjects with asymptomatic moderate to severe ARIA-E in each treatment group, a sample size of approximately 500 subjects is selected to provide a preliminary estimate of incidence rates. The sample size may be re-estimated based on evolving learning from external sources and blinded review of this study. Subjects will be randomized in a 1:1 ratio to each of the 2 treatment groups. When 1 clinically impactful ARIA event is observed, the incidence rate will be 0.004 and the 90% exact CI will be (0.0002, 0.0188). If 2 events are observed, the incidence rate will be 0.008 and the 90% exact CI will be (0.0014, 0.0250), and if 3 events are observed, the incidence rate will be 0.012 and the 90% exact CI will be (0.0033, 0.0307).

CONFIDENTIAL

The information contained herein may not be used, disclosed, or published without the written consent of Biogen MA Inc.

The assumed incidence rates and the probability of observing events in each group are presented in the following table.

Incidence Rate in Group 1	Incidence Rate in Group 2	Probability of Observing Same Number of Events in Group 1 and Group 2	Probability of Observing at Least 1 More Event in Group 2 vs. Group 1	Probability of Observing at Least 2 More Events in Group 2 vs. Group 1	Probability of Observing at Least 3 More Events in Group 2 vs. Group 1
1%	1%	18%	41%	24%	13%
1%	2%	10%	77%	64%	49%
1%	3%	3%	93%	87%	79%

CONFIDENTIAL

The information contained herein may not be used, disclosed, or published without the written consent of
Biogen MA Inc.

17. ETHICAL REQUIREMENTS

Biogen, Biogen designee, and the Investigator must comply with all instructions, regulations, and agreements in this protocol and applicable International Council for Harmonisation (ICH) and Good Clinical Practice (GCP) guidelines and conduct the study according to local regulations.

The Investigator may delegate responsibilities for study-related tasks where appropriate to individuals sufficiently qualified by education, training, and experience, in accordance with applicable ICH and GCP guidelines. The Investigator should maintain a list of the appropriately qualified persons to whom significant study-related duties have been delegated. The Investigator is responsible for supervising those individuals and for implementing procedures to ensure the integrity of the tasks performed and any data generated.

17.1. Declaration of Helsinki

This study will be performed in alignment with the ethical principles outlined in the Declaration of Helsinki.

17.2. Ethics Committee

The Investigator must obtain ethics committee approval of the protocol, ICF, and other required study documents prior to starting the study. Biogen will submit documents on behalf of the investigational sites worldwide in compliance with local requirements.

If the Investigator makes any changes to the ICF, Biogen must approve the changes before the ICF is submitted to the ethics committee. A copy of the approved ICF must be provided to Biogen. After approval, the ICF must not be altered without the agreement of the relevant ethics committee and Biogen.

It is the responsibility of the Investigators to ensure that all aspects of institutional review are conducted in accordance with current applicable regulations.

Biogen must receive a letter documenting ethics committee approval, which specifically identifies the protocol, protocol number, and ICF, prior to the initiation of the study. Protocol amendments will be subject to the same requirements as the original protocol.

A progress report must be submitted to the ethics committee at required intervals and not less than annually.

At the completion or termination of the study, the study site must submit a close-out letter to the ethics committee and Biogen.

CONFIDENTIAL

The information contained herein may not be used, disclosed, or published without the written consent of Biogen MA Inc.

17.3. Subject Information and Consent

Prior to performing any study-related activities under this protocol, including screening tests and assessments, written informed consent with the approved ICF must be obtained from the subject or subject's legally authorized representative, as applicable, in accordance with local practice and regulations. (The subject's informant/care partner may or may not be the subject's legally authorized representative.) Subjects can complete the neurocognitive scales (CDR and MMSE) as well as ApoE genotyping as an initial optional screening under a separate consent process. If the subject meets inclusion criteria for these 2 scales, the full consent process must be completed prior to the administration of further screening assessments. Subjects may also proceed directly to the full consent process that would allow the administration of all screening assessments.

The background of the proposed study, the procedures, the benefits and risks of the study, and that study participation is voluntary for the subject must be explained to the subject (or the subject's legally authorized representative). The subject must be given sufficient time to consider whether to participate in the study.

Subjects will be informed that their race and ethnicity will be collected during the study (unless the collection is not permitted by applicable law or not approved by the governing ethics committee) and the data will be used during analysis of study results.

A copy of the signed and dated ICF must be given to the subject or the subject's care partner/legally authorized representative. The original signed and dated ICF will be retained with the study records. Local regulations must be complied with in respect to the final disposition of the original (wet signature) and copies of the signed and dated ICFs.

Confirmation of informed consent must also be documented in the subject's medical record.

17.4. Subject Data Protection

Prior to any testing under this protocol, including screening tests and assessments, candidates must also provide all authorizations required by local law (e.g., Protected Health Information authorization in North America).

During the study, subjects' race and ethnicity will be collected (unless the collection is not permitted by applicable law or not approved by the governing ethics committee). These data will be used in the analysis of the safety and/or PK profile of the study treatment. It is unknown whether the effects of the study treatment are influenced by race or ethnicity.

Study reports will be used for research purposes only. The subject will not be identified by name in CRFs, study-related forms, study reports, or any related publications. Biogen, its partners and designees, ethics committees, and various government health agencies may inspect the records of this study. Every effort will be made to keep the subject's personal medical data confidential.

CONFIDENTIAL

The information contained herein may not be used, disclosed, or published without the written consent of
Biogen MA Inc.

17.5. Compensation for Injury

Biogen maintains appropriate insurance coverage for clinical studies and will follow applicable local compensation laws.

17.6. Conflict of Interest

The Investigators should address any potential conflicts of interest (e.g., financial interest in Biogen or its partner[s]) with the subject before the subject makes a decision to participate in the study.

17.7. Registration of Study and Disclosure of Study Results

Biogen will register the study and post study results regardless of outcome on a publicly accessible website in accordance with the applicable laws and regulations.

CONFIDENTIAL

The information contained herein may not be used, disclosed, or published without the written consent of Biogen MA Inc.

18. ADMINISTRATIVE PROCEDURES

18.1. Study Site Initiation

The Investigator must not screen any subjects prior to completion of a study initiation visit, conducted by Biogen. This initiation visit will include a detailed review of the protocol and study procedures.

18.2. Quality Control and Quality Assurance

Quality control procedures will be implemented at each stage of data handling to ensure that all data are reliable and have been processed correctly. Data anomalies will be communicated to the sites for clarification and resolution, as appropriate. The Investigator is responsible for endorsing all CRF data prior to any interim or final database lock.

During and/or after completion of the study, quality assurance officers named by Biogen or the regulatory authorities may wish to perform onsite audits or inspections. The Investigator will be expected to cooperate with any audit or inspection and to provide assistance and documentation (including source data) as requested.

18.3. Monitoring of the Study

The Investigator must permit study-related monitoring by providing direct access to source data and to the subjects' medical histories. Source data must be attributable, legible, contemporaneous, original, accurate, and complete. Changes to source data must be traceable, not obscure the original entry, and be explained if necessary (e.g., with an audit trail). The Investigator should maintain a record of the location(s) of essential documents.

The Clinical Monitor will visit the study site at regular intervals during the study and after the study has completed, as appropriate. A clinical site monitoring plan will detail who performs the monitoring, how often, and the extent of review. It also will provide the monitoring strategy, with emphasis on subject safety, data integrity, and critical data and processes.

During these visits, CRFs, supporting documentation, and essential documentation related to the study will be reviewed and any discrepancies or omissions will be resolved. Documentation of results will be provided to Biogen in a timely fashion to allow follow-up and verification of compliance with the monitoring plan. Remote evaluation of data (centralized monitoring) may also be conducted and reported as defined in the monitoring plan.

Monitoring visits must be conducted according to the applicable ICH and GCP guidelines to ensure the protection of subject rights and well-being, protocol adherence, quality of data (accurate, complete, and verifiable), study treatment accountability, compliance with regulatory requirements, and continued adequacy of the investigational site and its facilities.

CONFIDENTIAL

The information contained herein may not be used, disclosed, or published without the written consent of Biogen MA Inc.

18.4. Study Funding

Biogen is the Sponsor of the study and is funding the study. All financial details are provided in the separate contracts between the institution, Investigator, and Biogen.

18.5. Publications

Details are included in the clinical trial agreement for this study.

CONFIDENTIAL

The information contained herein may not be used, disclosed, or published without the written consent of
Biogen MA Inc.

19. FURTHER REQUIREMENTS AND GENERAL INFORMATION

19.1. External Contract Organizations

Biogen will ensure oversight of any study-related duties and functions carried out on its behalf and will specify in writing all duties and functions that are transferred.

19.1.1. Contract Research Organization

A CRO will be responsible for administrative aspects of the study including, but not limited to, study initiation, monitoring, and management of SAE reports. Before subjects are screened at each study site, the CRO will review study responsibilities with the Investigators and other study site staff, as appropriate.

19.1.2. Interactive Response Technology

IRT will be used in this study. Before subjects are screened or randomized, the IRT vendor will provide each study site with appropriate training, access rights, and a user manual.

19.1.3. Electronic Data Capture

Subject information will be captured and managed by study sites on electronic CRFs by a web-based electronic data capture (EDC) tool developed by a Biogen designee and configured by the EDC vendor.

19.1.4. Central Laboratories for Laboratory Assessments

Biogen has selected a central laboratory service to perform all standard hematology, blood chemistry, and urinalysis testing for the study. This central laboratory will also receive, track, and ship all urine and blood samples, and DNA for specialized ApoE ε4 genotyping, PK, [REDACTED], and ADA testing, including aliquots from these samples retained as backup in case original samples are lost or not evaluable. Blood samples collected [REDACTED] stored by the central laboratory.

Laboratories performing specialized testing will be identified in regulatory documentation. These laboratories will use appropriately validated or qualified assays to test study samples.

19.1.5. Central Facility for Other Assessments

A central imaging laboratory has been selected by Biogen to read and interpret all MRIs for this study within the timeframe specified in the procedural manual for MRI. In cases of ARIA-E and ARIA-H, the central imaging laboratory must expedite notification to the PI and Biogen. For the purposes of study conduct, the MRI interpretations from the central reader will prevail over those from the local radiologist.

CONFIDENTIAL

The information contained herein may not be used, disclosed, or published without the written consent of Biogen MA Inc.

The central imaging laboratory will also collect PET scans and assess the screening scan for eligibility criteria.

19.1.6. Neurocognitive Assessments

Biogen selected a rater management group to establish rater qualification, study-specific training, and oversight. The study raters are required to complete qualifications steps and required training prior to administering study assessments. The rater management group will oversee the assessments per project-specific plans. All neurocognitive data, with the exception of DSST and MoCA assessments, will be captured via electronic means.

19.2. Study Committees

19.2.1. Adjudication Committee

The Adjudication Committee will be formed to review all symptomatic ARIAs and ARIAs reported as SAEs, and adjudicate if any event meets the criteria of the primary endpoint. The adjudication process is considered independent of AE/SAE data collection and analysis.

An Adjudication Committee charter will provide full guidance on the function and practices to be followed.

19.2.2. Data Safety Monitoring Committee

The DSMC will be formed to review ongoing safety data. Members of the DSMC will not be allowed to participate as Investigators in this study.

The DSMC will review safety data on an ongoing basis to ensure safe and proper treatment of subjects, assess the safety of the study interventions, and monitor the overall conduct of the study. The DSMC, based on the nature, frequency, and/or severity of any adverse events, may recommend protocol modification(s), dose suspension, dose termination, or study termination. In addition, during the study, the DSMC will make a recommendation to continue dosing in subjects with asymptomatic severe ARIA in Group 2. This may be triggered as early as when the first 150 subjects have had the opportunity to complete at least 6 months of treatment, or when the first 20 asymptomatic subjects have completed at least 2 additional doses since the initial identification of ARIA (ARIA-E with or without ARIA-H, or isolated ARIA-H), as moderate in severity, whichever occurs first.

A DSMC charter will provide full guidance on the function and practices to be followed.

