4.3.2.1.3. Study 221AD103

Currently available data on ARIA are mostly based on the ongoing Study 221AD103 of aducanumab in subjects with prodromal AD or mild AD dementia. This study comprises a completed double-blind, 1-year placebo-controlled period, followed by an ongoing LTE in which all subjects receive aducanumab via monthly infusions, in a dose-blinded fashion. A total of 185 subjects have been dosed with aducanumab, in the placebo-controlled period and/or the LTE.

Based on data available as of 25 May 2017 in a prespecified interim analysis, ARIA-E (with or without ARIA-H) has been detected in 25% of all aducanumab-treated subjects (46/185). In the 12-month placebo-controlled period, in subjects receiving aducanumab in a fixed-dose regimen,

CONFIDENTIAL

The information contained herein may not be used, disclosed, or published without the written consent of Biogen MA Inc.

the incidence of ARIA-E increased with dose and was higher in ApoE ε4 carriers than noncarriers (3% [1/31], 6% [2/32], 37% [11/30], and 41% [13/32] in the 1, 3, 6, and 10 mg/kg dose groups, respectively). However, the incidence of ARIA-E appeared to be lower in ApoE ε4 carrier subjects receiving titration to 10 mg/kg (35% [8/23]) than in carrier subjects receiving fixed doses (43% [9/21] and 55% [11/20]) of 6 and 10 mg/kg, respectively. Furthermore, among the 8 ApoE ε4 carrier subjects receiving titration to 10 mg/kg who had ARIA-E, the abnormalities were observed at the 3 and 6 mg/kg dose levels (5 and 3 subjects, respectively).

The incidence of isolated ARIA-H was similar in the placebo and aducanumab groups (7% [3/46] and 5% [7/148], respectively), which likely indicates a background finding in this population.

ARIA was typically observed early in the course of the treatment, with the majority of cases observed between the second and fifth doses. A total of 91% of subjects (42/46) developed the first episode of ARIA-E within the first 12 months of active dosing, with 76% of subjects (35/46) developing the first episode within the first 6 months of active dosing. In most cases, ARIA-E resolved 4 to 12 weeks after onset as assessed by MRI, and ARIA-H was typically stable within 2 to 4 weeks after onset.

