11.1.2. Placebo

All subjects receive aducanumab in this study.

To maintain the blind to subjects' group assignment, subjects in Group 1 who have asymptomatic ARIA (except macrohemorrhage) that requires dose suspension or discontinuation of active dosing as per protocol will receive placebo. Placebo (0.9% sodium chloride) will be supplied by the study site.

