Clinical Symptom Severity (if present)	New Incident ARIA-H Severity on MRI (Central Read) ¹		
	Mild	Moderate	Severe
Microhemorrhage	≥1 and ≤4	≥5 and ≤9	≥10
Superficial siderosis	1	2	>2
Asymptomatic	Stage 1		
Group 1	Continue dosing at current dose and schedule	Suspend dosing and receive placebo. Once ARIA-H is stable, the subject may resume dosing at the same dose.	Permanently discontinue treatment ³
Group 2	Continue dosing at current dose and schedule ²		
Asymptomatic	Stage 2		
Group 1	Continue dosing at current dose and schedule	Suspend dosing and receive placebo. Once ARIA-H is stable, the subject may resume dosing at the same dose.	Permanently discontinue active dosing and receive placebo ³
Group 2	Continue dosing at current dose and schedule ²		
Symptomatic	Throughout Study, Groups 1 and 2		
Mild	Suspend dosing. Once ARIA-H is stable and clinical signs and symptoms resolve, the subject may resume dosing at the same dose.	Permanently discontinue treatment ³	
Moderate			
Severe			
Serious, “other medically important event” only ⁴			
Serious, “hospitalization” only	Suspend or permanently discontinue treatment at treating HCP’s discretion. In case of dosing suspension, once ARIA-H is stable and clinical signs and symptoms resolve, the subject may resume dosing at the same dose.	Permanently discontinue treatment ³	
Serious, except for “other medically important event” and “hospitalization” ⁵	Permanently discontinue treatment ³		

¹“New incident microhemorrhages” refers to new incident microhemorrhages while subject is receiving study treatment; does not include microhemorrhages observed at baseline.

²In Group 2, dosing initially (Stage 1) will be continued in mild and moderate cases only. After a review of the Stage 1 data and based on recommendation from the DSMC, dosing will be continued in Stage 2 regardless of severity (Section 19.2.2).

³Subjects who permanently discontinue treatment are to remain in the study and follow a modified schedule for tests and assessments until the end of study or withdrawal of consent (Table 4). The only exception is a subject who

CONFIDENTIAL

The information contained herein may not be used, disclosed, or published without the written consent of Biogen MA Inc.

may develop severe asymptomatic ARIA-H in Stage 2 as outlined in Table 6; such a subject is to follow the regular visit schedule (Table 1) to maintain the blind to the subject's group assignment.

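### Does it matter that Section 19.2.2 does not say whether Group 1 subjects on placebo count towards the 20 moderate ARIA cases that can open the DSMC review?

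*Protocol*

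**What the plan says.** Section 19.2.2 asks the DSMC, during the study, for a recommendation on continued dosing in Group 2 subjects with severe asymptomatic ARIA. It gives two conditions and takes the earlier.

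- Enrolment condition: "This may be triggered as early as when the first 150 subjects have had the opportunity to complete at least 6 months of treatment".
- Case-count condition: "when the first 20 asymptomatic subjects have completed at least 2 additional doses since the initial identification of ARIA" as moderate in severity. ARIA-E with or without ARIA-H, and isolated ARIA-H, all qualify.

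Group 2 is named in the sentence before, as the target of the recommendation, but not in the count. The section ends by leaving the committee's function and practices to a DSMC charter, which is not among the documents.

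The two groups are treated differently after moderate asymptomatic ARIA. Group 2 continues aducanumab. For Group 1, Table 6 in Section 11.2.1.2 says "Suspend dosing and receive placebo. Once ARIA-H is stable, the subject may resume dosing at the same dose", and Table 5 does the same for ARIA-E. Section 11.1.2 confirms that Group 1 asymptomatic ARIA "that requires dose suspension or discontinuation of active dosing as per protocol will receive placebo".

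Section 16.7 sizes the trial to "enroll 25 subjects with asymptomatic moderate to severe ARIA-E in each treatment group, a sample size of approximately 500 subjects".

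**The concern.** Stage 1 compares continued dosing with suspension, and only Group 2 moderate cases are exposed to continued dosing. A reader could take 20 as the number of subjects dosed through moderate ARIA before the committee considers severe ARIA. The text does not secure that. Three readings are open:

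1. both groups count, and a placebo infusion is a dose;
2. both groups count, but Group 1 only after aducanumab is resumed;
3. only Group 2 counts.

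At stake would be how much the Stage 1 evidence can exclude. If an event type is not seen in n subjects, the one-sided 95% upper limit for its rate is 1 − 0.05^(1/n): 14% for n = 20, 26% for n = 10, 28% for n = 9 and 35% for n = 7. A decision thought to rest on 20 subjects but resting on 7 to 10 would be noticeably weaker. The reading also affects who can call the trigger, since a Group 2 count needs access to treatment assignment.

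**Working it through.** **The plan's own figures.** The exact 90% intervals in Section 16.7 for 1, 2 and 3 events in 250 reproduce: (0.0002, 0.0188), (0.0014, 0.0250) and (0.0033, 0.0307). The 500 does not follow exactly from the Study 221AD103 counts. With 21 moderate or severe asymptomatic ARIA-E cases in 185, N = 2 × 25/(21/185) = 440.5. At 500 the expectation is 250 × 21/185 = 28.4 per group, so 500 is on the cautious side. The trigger numbers 150 and 20 have no stated derivation to reproduce.

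**Rates.** Section 16.7 reports "20 subjects developed asymptomatic moderate ARIA-E and 1 subject developed severe asymptomatic ARIA-E" among 185 subjects, so the moderate asymptomatic ARIA-E rate is 20/185 = 10.8%. Section 4.3.2.1.3 adds: "The incidence of isolated ARIA-H was similar in the placebo and aducanumab groups (7% [3/46] and 5% [7/148], respectively". The moderate share of isolated ARIA-H is not given. Treating all of it as moderate and asymptomatic gives an upper bound of 10.8% + 4.7% = 15.5%.

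**If the case count opens the review, pooled.** With 1:1 randomization the Group 2 share of 20 is Binomial(20, 0.5): mean 10, 95% range 6 to 14.

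**If the enrolment condition opens the review.** Of 150 subjects, 75 are in Group 2. Suppose every case in them has been found and followed by two infusions:

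| Rate | Cases in 150 | Cases in 75 | P(at least 20 in 150) | P(at least 20 in 75) |
|---|---|---|---|---|
| 10.8% | 16.2 | 8.1 | 0.19 | 0.0001 |
| 15.5% | 23.3 | 11.7 | 0.80 | 0.009 |

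**How demanding is a Group 2 count of 20?** Against the planned 25 per group it is 20/25 = 80%, while 150 of 500 is 30%. The first ratio is not like for like, because the 25 are moderate-to-severe ARIA-E only and the trigger also counts isolated ARIA-H. Using expected moderate cases, 250 × 20/185 = 27.0 and 20/27.0 = 74%. Adding all isolated ARIA-H, 250 × 7/148 = 11.8 and 20/(27.0 + 11.8) = 51%. The enrolment condition still normally comes first.

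**Simulation of the earlier event.** Settings:

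- 500 subjects, 250 per group, with accrual assumed at 10 to 100 per month, since the documents give no rate.
- First onset follows Section 4.3.2.1.3, "with 76% of subjects (35/46) developing the first episode within the first 6 months of active dosing", and 42/46 = 91% by 12 months.
- A case is identified either at the next scheduled MRI, with two infusions complete 4 weeks later, or at onset, with two infusions complete 8 weeks later.
- The enrolment condition is met 26 weeks after the 150th entry.

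Mean number of Group 2 subjects with two further infusions when the review can first open:

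| Rate | Pooled, placebo counted | Group 2 only |
|---|---|---|
| 10.8% | 6.6 to 8.6 | 6.7 to 9.1 |
| 15.5% | 9.0 to 9.9 | 9.8 to 12.9 |

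Setting by setting, the readings differ by at most 9.1 − 8.6 = 0.5 subject at 10.8% and 12.9 − 9.9 = 3.0 at 15.5%. The Group 2-only count reached 20 first in at most 4% of runs. With all 500 enrolled at once, the Group 2-only mean rises to between 11.1 and 17.7, and at the 15.5% rate up to 44% of runs reach 20 first.

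Which condition comes first depends heavily on detection. At 10.8%, a pooled count comes first in about 1% to 10% of runs with scheduled scans only and 4 or 8 weeks to the second infusion. That rises to about 63% if ARIA is identified at onset, the second infusion follows within 4 weeks and accrual is fast. Under reading 2, with scheduled scans and aducanumab resumed after 4 to 12 weeks, the count comes first in 1% to 6% of runs at 10.8% and 17% to 50% at 15.5%.

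**The case for a change.** The case for a change is that the wording is open and cheap to close. Other sections do not settle it, and the protocol uses dose both ways: Tables 5 and 6 treat Group 1 moderate cases as suspended, while Section 11.2.4 times MRI by every second dose and includes subjects who are receiving placebo. Sites and ethics committees read the protocol, not the charter. One clause would do, and the SAP's differential study treatment population (SAP Section 2.3) shows how to separate the groups.

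Much of this stands: the text is silent, and fewer than 20 dosed-through subjects are expected. What does not stand is the inference that something must be corrected.

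- The trigger sets when the review may begin, not what it must contain. Nothing ties the recommendation to 20 subjects, and the committee can wait for more cases.
- The literal wording has no group restriction, and a pooled count suits a comparison in which Group 1 cases are the concurrent control.
- Section 11.2.1 has the DSMC reviewing comprehensive ARIA information throughout. A recommendation about Group 2 requires looking at Group 2, so a formal line giving its count and upper limit adds little.
- Blinding is not an obstacle. Section 9.3 exempts pharmacy staff and designated sponsor personnel, and under Section 11.2.1 the interactive response system already combines symptoms, central MRI reads and group assignment.

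**Conclusion.** This is missing detail of a kind a DSMC charter ordinarily supplies. Section 19.2.2 does not say whether the 20 are pooled or Group 2 only, or whether placebo infusions count. Pooled, about 10 of the 20 (6 to 14) would be dosed-through Group 2 subjects. With Group 2 only, the enrolment condition normally comes first, with roughly 5 to 11 such subjects at 10.8% and 8 to 15 at 15.5% across the accrual and detection assumptions tried.

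These figures assume that the Study 221AD103 rates, which pool several dose groups, carry over, and that accrual is within the assumed range. They are expectations at the earliest permitted time. About 27 moderate ARIA-E cases would be expected across all 250 Group 2 subjects.

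No change is needed. Choosing either reading would barely move the expected Group 2 exposure at 10.8%, and by about 3 subjects at the upper-bound rate with accrual of 10 to 100 per month. It would alter no endpoint, interval or conclusion. It also has no present effect: the SAP Introduction records that enrolment and dosing were halted on termination, and SAP Section 2.5.2.2 says the primary endpoint will not be evaluated.
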